3.2 Schedule of Study Procedures

Table 1. Schedule of Assessments

	Screening	If Eligible, Baseline Assessment	R	SFISD	24 (±1) Hours ⁱ	48 (±1) Hours ⁱ	72 (±2) Hours	96, 144, 192, 240 (±4) Hours ^{h,k}	120, 168, 216 (±4) Hours ^{h,k}	Days 12- 28 Q48 (±4) Hours ^{h,k}	Day 30 (±5) Days
Informed Consent	X										
Demographics	X										X^{l}
Medical History	X										
List of Medications	X										
Concomitant Meds				X	X	X	X	X	X		X
Height		X									
Weight		X					X				X
Vital Signs	X				X	X	X	X	X		X
Abdominal Exam	X										
PNRS		X			X	X	X	X	X		X
Serum Lipase	Xa										
CBC+diff+Platelets	Xa				Xa	Xª	Xa		Xa		Xª
Presence of SIRS ^b	X										
SpO ₂ +FiO ₂		X			X	X	X	X	X		X
CECT of Pancreas ^c	X										X
Serum Pregnancy Test	X ^a										
Randomize Patient ^d			X								
Serum Chemistries		X ^a			X ^a	Xª	X ^a		X ^a		Xª
Serum Procalcitonin		X ^a			Xa	Xª	Xª		X ^a		Xª
Serum Biomarker ^e		X			X	X	X		X		X
Urine Biomarker ^e		X			X	X	X		X		X
Administer Study Drug				X	Xi	Xi					

Protocol CM4620-203 CONFIDENTIAL Page 8 of 31

CalciMedica Inc.		Prot	ocol No	. CM462	0-203		St	atistical A	nalysis P	lan	
PK sample ^e				X^{j}	\mathbf{X}^{j}		X^{j}				\mathbf{X}^{j}
Medically Indicated Discharge Criteria ^f					X	X	X	X	X	X	X
Enhanced Recovery Strategy ^g				X	X	X	X	X	X	X	X ^m
mGCSI-DD ^h		X ^h					X^h			X ^h	X ^h
AE/SAE Evaluation			X	X	X	X	X	X	X	X	X
Telephone Contacts, as needed	Following patient discharge, Investigator or designee should contact patient at least once weekly to confirm diary completion, Day 30 visit schedule and assess for AE/SAEs.										

AE = adverse event; CECT = contrast-enhanced computed tomography; PK = pharmacokinetics; mGCSI-DD = Modified American Neurogastroenterology and Motility Society Gastrointestinal Cardinal Symptom Index Daily Diary; PI = Principal Investigator; PNRS = Pain Numeric Rating Scale; SAE = serious adverse event; SFISD = Start of First Infusion of Study Drug

- a. Blood sample for serum pregnancy test, serum lipase and CBC+diff+Platelets at Screening will be analyzed at local laboratory. May use results obtained as standard of care if blood drawn in the previous 12 hours prior to consent or following consent but prior to randomization. Following screening, all protocol-required blood samples, except as noted in Footnote "e", will be analyzed at local laboratory. Baseline blood samples including biomarkers may be performed on blood drawn in the previous 12 hours of randomization. For all later assessment times, blood drawn in the previous 12 hours maybe used (except PK).
- b. The most extreme value for each criterion in the 24 hours before consent or following consent but prior to randomization may be used.
- c. A CECT already performed in the 24 hours prior to the patient or LAR providing informed consent may be used as the Screening CECT. In addition to the Screening and the Day 30 visit CECTs, CECTs performed as standard of care after randomization and to 25 days after SFISD will be captured and submitted for central reading. If the CECT is performed 25 to 29 days after SFISD, it will substitute for the Day 30 visit CECT scan and will be captured.
- d. Hematocrit collected as standard of care within 12 hours of consent or following consent but prior to randomization may be used for Inclusion Criterion 3c.
- e. Biomarker blood and urine samples and blood samples for PK will be analyzed at central laboratory. If site or patient does not participate in these assessments this will be documented at start of study and will not be considered a protocol deviation.
- f. Determine if patient had met the medically indicated discharge criteria within the prior 24- or 48-hour visit assessment.
- g. Patients will be offered a low fat, ≥500-calorie solid meal at each mealtime after the infusion of the first dose of study drug until discharge if alert and not on mechanical ventilation, or if not NPO for a planned surgery/medical procedure, or if not NPO because of an a cute medical condition. If the patient does not wish to eat the solid meal when offered or is unable to tolerate the solid meal, they should then be offered a liquid meal. Determine for each meal if the patient ate ≥50% of the meal without vomiting or having abdominal pain in the two hours after the meal
- h. The mGCSI-DD score will be completed by all eligible patients at the baseline assessment and on the day of discharge, which will vary by patient as shown in schedule above. In addition, if the patient remains hospitalized at 96 and/or 168 hours and/or at Day 14 and/or Day 21 patient should be requested to record their symptoms at bedtime using the mGCSI-DD worksheet. Patients will be trained on completing the mGCSI-DD worksheet. Upon discharge, patient will record the mGCSI-DD score daily before bedtime until the Day 30 visit.
- i. In the scenario where the PI or treating physician wants the infusion(s) to begin earlier than the 24 +/- 1 hour window, the PI or treating physician should contact the medical monitor to discuss whether it is appropriate to begin infusion earlier (up to 6 hours earlier) than the 24 +/- 1 hour protocol window.
- j. Blood samples for PK analysis will be drawn as soon as possible after the completion of the first infusion of study drug (wit hin +2 hours), prior to the start of second infusion of study drug (within -30 min), at 72 hours (±2 hours) from the SFISD, and at the Day 30 visit. If the patient is discharged after the third infusion of study drug and prior to 72 hours from the SFISD, the blood sample will be drawn prior to discharge.
- k. Study assessments continue daily, or every other day, as noted in schedule of events until discharge or the Day 30 visit. All patients return for Day 30 assessments if discharged earlier than Day 25.
- 1. At the Day 30 visit (or at the time of death if before Day 30), record the Investigator's opinion on the etiology of the episode of AP. m. Only patients who remain hospitalized at Day 30.

4. SAMPLE SIZE

A sample size of 216 patients will be randomized into four groups on a 1:1:1:1 basis, resulting in 54 patients randomized into each group. This sample size will provide 86% power for testing the difference in two populations having a median length of time of 72 and 144 hours, respectively, to tolerating solid food. This sample size will provide 80% power with a two-sided alpha of 0.05 to detect a 45% response rate for tolerating solid food in an Auxora dose group versus a 20% response rate in the placebo group in the 72 hours after completion of the first study drug infusion.

Protocol CM4620-203 CONFIDENTIAL Page 9 of 31

5. STUDY ENDPOINTS

5.1 Efficacy Endpoints:

- Primary endpoint
 - o Time to solid food tolerance
- Secondary endpoints:
 - Solid food tolerance at 48 hours, 72 hours, and 96 hours after the Start of First Infusion of Study Drug (SFISD) and at discharge
 - Time to medically indicated discharge
 - o Length of stay in the hospital
 - o Length of stay in the intensive care unit (ICU) for patients admitted to the ICU
 - o Re-hospitalization for acute pancreatitis (AP) by Day 30
 - o Change in severity of AP by CTSI score from screening to Day 30
 - o Development of pancreatic necrosis ≥30% and >50%
 - The persistence of SIRS ≥48 hours after the SFISD
 - o Incidence, severity, and duration of organ failure
 - o Mortality by Day 30
 - o Change in pain score and opioid use
- Exploratory endpoints:
 - o Development of infected pancreatic necrosis
 - Development of sepsis
 - o Hospital procedures for the management of pancreatic necrosis
 - Change in GCSI-DD score
 - o Change in albumin
 - o Change in absolute neutrophil count (ALC)/absolute lymphocyte count (ALC) ratio
 - o Change in IL-6 levels
 - o Change in urine neutrophil gelatinase-associated lipocalin (NGAL) levels

5.2 Safety Endpoints:

- The incidence of TEAEs and SAEs
- The intensity and relationship of TEAEs and SAEs
- Clinically significant changes in vital signs and safety laboratory results

5.3 Proof of Concept Composite Efficacy Endpoint:

The proof-of-concept efficacy analysis uses a hierarchical combination applying the method of Finkelstein-Schoenfeld (Finkelstein 1999) to:

- All-cause mortality at Day 30 Visit, and
- Persistent severe respiratory failure through Day 30 Visit, and
- Pancreatic necrosis ≥30% through Day 30 Visit, and
- Rehospitalization for AP through Day 30 Visit, and
- Time to solid food tolerance within 30 Days of the study

Protocol CM4620-203 CONFIDENTIAL Page 10 of 31

6. ANALYSIS POPULATION(S)

6.1 Efficacy and Safety

The efficacy analyses will be performed on the Modified Intent-to-treat Population (MITT) consisting of all randomized patients who receive any amount of study drug. The safety analyses will be performed on the MITT data set.

7. TIMINGS OF ANALYSES

7.1 Final Analysis

The final analysis will be conducted when all randomized patients complete the study.

8. STATISTICAL ANALYSIS

8.1 General Considerations

The statistical evaluation will be performed using SAS® Version 9.4 or later.

In general, descriptive statistical methods will be used to summarize the data from this study. Unless stated otherwise, the term "descriptive statistics" refers to number of patients (n), mean, median, standard deviation (SD), standard error (SE), minimum and maximum for continuous data, interquartile ranges for nonparametric data, and frequencies and percentages for categorical data. Safety and efficacy summaries will be performed on the efficacy and safety analysis sets, respectively.

8.1.1 Number of Digits to Report

Table 2. Number of Decimal Places (DP)

Statistic	Specification	Apply to
Minimum, maximum	Same number of DPs as the	All original, i.e., non-derived,
	data provided in the datasets	data provided in the datasets
mean, median, confidence	One more DP than the raw	All
intervals	data	
SD, SE	Two more DP than the raw	All
	data	
Percentages	1 DP	All
p-values	3 DP	All
Odds Ratio	2 DP	All
Hazard Ratio	3 DP	All

8.1.2 Significance Level and Confidence Interval

The statistical tests will be performed as two-sided with significance level of 5% unless specified otherwise. The confidence intervals will be determined with a confidence level of 95%.

Protocol CM4620-203 CONFIDENTIAL Page 11 of 31

8.1.3 Descriptive Statistics Values to Calculate

Where appropriate, variables will be summarized descriptively (frequency and percent will be summarized for categorical variables; mean, SD, median, minimum, and maximum will be presented for continuous variables) by study visit, and by treatment group.

The denominator for the percentages will be the total number of subjects in the treatment group and Analysis Set being presented, unless otherwise specified (e.g., on some occasions, percentages may be calculated based on the total number of subjects with available data at a particular visit and/or time point).

8.1.4 Derived Variables

8.1.4.1 Definition(s) of Baseline(s)

Unless otherwise specified, the baseline values are the last available assessment before or at the time of the SFISD. If multiple measurements are recorded on the same day, the last measurement recorded prior to or at the time of the SFISD will be used as the baseline value. If these multiple measurements occur at the same time or time is not available, then the average of these measurements (for continuous data) or the worst among these measurements (for categorical data) will be considered as the baseline value.

8.1.4.2 Study Time

For patients enrolled in the study, the first dose of study medication will be administered at study hour 0. The study time in hours for an event is defined as event date and time – date and time of SFISD. The study day is defined as event date – date of SFISD + 1 day.

8.1.4.3 Definition(s) of (Percent) Change from Baseline(s)

For numerical variables, change from baseline will be calculated as the post-baseline value minus the baseline value. If percent change from baseline is required, then percent change from baseline will be calculated as the change from baseline divided by the baseline value, multiplied by 100. If baseline value cannot be determined for a particular variable, the change from baseline and percent change from baseline will not be calculated.

8.1.4.4 Adverse Events

Treatment-emergent AEs (TEAEs) are defined as AEs that started or worsened in severity on or after the SFISD. All adverse events will be coded from the reported term using the Medical Dictionary for Regulatory Activities (MedDRA) version 23.0 or the later version.

8.1.4.5 Concomitant Medications

All concomitant medications will be coded using the WHO drug dictionary (B3 WHO Drug Dictionary Enhanced – Sep 2019 or the later version).

Protocol CM4620-203 CONFIDENTIAL Page 12 of 31

8.1.4.6 Lab Values Below/Above the Limit of Quantitation Deriving

The lab values below the limit of quantification (BLQ) are collected in the form like "<2" in the clinical database. In this case the numeric value of the lab is a missing value. The cut-off value '2' will be used to impute the missing value for this case. Similarly, for the lab values above the limit of quantification, the cut-off value will be used for the numeric value of the lab. Local labs are used in this study and all lab parameters will be standardized to common SI units.

8.1.5 Missing Data for Safety Endpoints and Concomitant Medications

Missing data will not be imputed in the summary of safety endpoints at each time point. Imputation of missing or incomplete dates will be performed on AEs and concomitant medications (procedures) conservatively for determining the timing relative to the dose of study product unless otherwise specified. Partial or missing dates will be listed as recorded in the electronic case report form (eCRF).

8.1.6 Study Visits

The study summary and analysis will be based on the eCRF visits.

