(±1 hour) for a total of three doses. Patients randomized to Group 2 will receive 1.0 mg/kg of Auxora intravenously every 24 hours (±1 hour) for a total of three doses. Patients randomized to Group 3 will receive 0.5 mg/kg of Auxora intravenously every 24 hours (±1 hour) for a total of three doses. Patients randomized to Group 4 will receive emulsion without any active pharmaceutical ingredient. Patients in Group 4 will receive one of three randomly assigned dose volumes, 1.25 mL/kg, 0.625 mL/kg, or 0.3125 mL/kg, which will be administered intravenously every 24 hours (±1 hour) for a total of three doses. (Section 5.3) The dosing will be based on actual body weight obtained at the time of hospitalization or screening for the study. As described in the pharmacy manual, the upper limit of the volume of Auxora and volume of Placebo that will be administered will be 156.25 mL. The sponsor, investigators, pharmacists, and patients will be blinded to the assigned group. In the event of a medical emergency, investigators will be able to receive the treatment assignment if required to provide optimal care of the patient.

For all 4 groups, a study physician or appropriately trained delegate will perform study-specific assessments at screening, at the baseline assessment, immediately prior to the SFISD, and then every 24 hours until 240 hours after the SFISD, or until discharge if earlier. If patients remain hospitalized at Day 12, assessments will then be performed every 48 hours starting on Day 12 until Day 28, or until discharge if earlier. Patients discharged from the hospital before Day 25 will return at Day 30 (+5 days) to perform the Day 30 assessments. If patients are discharged on Days 25-29, the Day 30 assessments may be performed prior to discharge.

Patients will receive another CECT of the abdomen/pancreas at the Day 30 (± 5 days) visit. All CECTs performed as SOC after randomization and before the Day 30 CECT will also be captured. A blinded central reader will read the Screening, Day 30, and any SOC CECTs obtained between randomization and the Day 30 visit.

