8.10 Day 30 (±5 days)

Patients who had been discharged from the hospital before Day 25, should return on Day 30 for the following assessments:

- Record the investigator's opinion of etiology of the AP episode
- Record weight
- Perform CECT of the pancreas. May be performed in the 5 days before or after the visit.
- Collect mGCSI-DD worksheets from the patient
- Record concomitant medications
- Record vital signs
- Record the patient's pain using the PNRS
- Record SpO₂ and the FiO₂ (see Section 8.12.6)
- Perform AE/SAE assessment
- Draw blood samples for CBC, differential, platelets, Serum Procalcitonin, and Serum Chemistries - analyze at local lab
- Draw blood sample for Serum IL-6 send to central lab
- Draw a blood sample for PK send to central lab
- Obtain sample for Urine NGAL send to central lab

For patients discharged from the hospital on Days 25-29, the Day 30 assessments may be performed on the Day of discharge.

Patients who are discharged from the hospital on Days 25-29 will not complete the mGCSI-DD after discharge. They will only complete it on the day of discharge.

For patients who remain hospitalized on Day 30, the following additional assessment will be performed:

- Determine if, and when the patient tolerated solid food in the previous 48 hours
- Determine if the patient met the medically indicated discharge criteria in the previous 48 hours (see Section 5.3)

For patients that do not return for Day 30 visit and have not withdrawn consent, the Investigator or designee will continue to contact patient by phone to return for on-site visit up to eight weeks following visit date. Although an out of window visit assessment would be considered a protocol deviation, investigators should attempt to obtain as much as possible all of the Day 30 visit assessments, including the Day 30 CECT.

If patient is not reachable by phone after four weeks following the planned Day 30 visit, the Investigator or designee will send certified letter to last known address to request patient to contact Investigator to either schedule Day 30 visit or at least confirm patient is still alive by telephone. If patient does not respond to certified letter or if patient had withdrawn consent, the Investigator or designee will check public records (e.g., vital records search) to determine if the patient had died prior to the scheduled Day 30 visit or can be assumed alive for the purposes of study follow-up.

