- b. The most extreme value for each criterion in the 24 hours before consent or following consent but prior to randomization may be used.
- ^{c.} A CECT already performed in the 24 hours prior to the patient or LAR providing informed consent may be used as the Screening CECT. In addition to the Screening and the Day 30 visit CECTs, CECTs performed as standard of care after randomization and to 25 days after SFISD will be captured and submitted for central reading. If the CECT is performed 25 to 29 days after SFISD, it will substitute for the Day 30 visit CECT scan and will be captured.
- d. Hematocrit collected as standard of care within 12 hours of consent or following consent but prior to randomization may be used for Inclusion Criterion 3c.
- e. Biomarker blood and urine samples and blood samples for PK will be analyzed at central laboratory. If site or patient does not participate in these assessments this will be documented at start of study and will not be considered a protocol deviation.
- f. Determine if patient had met the medically indicated discharge criteria within the prior 24- or 48-hour visit assessment.
- Patients will be offered a low fat, ≥500-calorie solid meal at each mealtime after the infusion of the first dose of study drug until discharge if alert and not on mechanical ventilation, or if not NPO for a planned surgery/medical procedure, or if not NPO because of an acute medical condition. If the patient does not wish to eat the solid meal when offered or is unable to tolerate the solid meal, they should then be offered a liquid meal. Determine for each meal if the patient ate ≥50% of the meal without vomiting or having abdominal pain in the two hours after the meal.
- h. The mGCSI-DD score will be completed by all eligible patients at the baseline assessment and on the day of discharge, which will vary by patient as shown in schedule above. In addition, if the patient remains hospitalized at 96 and/or 168 hours and/or at Day 14 and/or Day 21 patient should be requested to record their symptoms at bedtime using the mGCSI-DD worksheet. Patients will be trained on completing the mGCSI-DD worksheet. Upon discharge, patient will record the mGCSI-DD score daily before bedtime until the Day 30 visit.

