randomized to Group 2 will receive 1.0 mg/kg (0.625 mL/kg) of Auxora intravenously every 24 hours (±1 hour) for a total of three doses. Patients randomized to Group 3 will receive 0.5 mg/kg (0.3125 mL/kg) of Auxora intravenously every 24 hours (±1 hour) for a total of three doses. Patients randomized to Group 4 will receive emulsion without any active pharmaceutical ingredient (placebo). Patients in Group 4 will receive one of three randomly assigned dose volumes, 1.25 mL/kg, 0.625 mL/kg, or 0.3125 mL/kg, which will be administered intravenously every 24 hours (±1 hour) for a total of three doses. The dosing will be based on actual body weight obtained at the time of hospitalization or screening for the study. As described in the pharmacy manual, the upper limit of the volume of Auxora and volume of placebo that will be administered will be 156.25 mL. The sponsor, investigators and patients will be blinded to the assigned group. In the event of a medical emergency, investigators will be able to receive the treatment assignment if required to provide optimal care of the patient.

For all 4 groups, a study physician or appropriately trained delegate will perform assessments at screening, at the baseline assessment, immediately prior to the SFISD, and then every 24 hours until 240 hours after the SFISD, or until discharge if earlier. If patients remain hospitalized at Day 12, assessments will then be performed every 48 hours starting on Day 12 until Day 28, or until discharge if earlier. Patients discharged from the hospital before Day 25 will return at Day 30 (+5 days) to perform the Day 30 assessments. If patients are discharged on Days 25-29, the Day 30 assessments may be performed prior to discharge.

Patients will receive another CECT of the abdomen/pancreas at the Day 30 (±5 days) visit. All CECTs performed as standard of care after randomization and before the Day 30 CECT will also be captured. A blinded central reader will read the Screening, Day 30, and any standard of care CECTs obtained between randomization and 30 days.

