8.7.3 Length of Stay in the Hospital

The number of days patients are in the hospital from the SFISD, including ICU stay and readmissions for any etiology, during the 30 Days of the study will be summarized by treatment groups and compared between each Auxora treatment group and placebo group using an analysis of variance model, which includes treatment group, the stratification factor of the eCRF recorded sex (male or female), and then the stratification factor of the risk for organ failure (higher or lower) based on eCRF data as the fixed effects in the model. The proportion of patients in each quartile of hospital stay (1-7 days, 8-14 days, 15-21 days, and 22-30 days) and the patients who remain hospitalized at Day 30 will also be summarized by treatment groups.

Two sets of analyses will be conducted. The first analysis is to assess patient benefit; the number of days in the hospital will be defined as 30 if the patient dies due to acute pancreatitis (composite strategy). The second analysis is to assess healthcare systems benefit; the number of days in the hospital before the patient's death will be used in the analysis (while alive strategy).

8.7.4 Re-hospitalization for acute pancreatitis (AP) Through Day 30

The date of each re-hospitalization and the reasons for re-hospitalizations will be collected for each patient. The proportion and 95% CI of patients who are re-hospitalized for either acute pancreatitis or the development of pancreatic necrosis/necrotizing pancreatitis through the Day 30 visit will be displayed using a Clopper-Pearson interval and will be compared between each Auxora treatment group and placebo group using a Cochran-Mantel-Haenszel test stratified by the sex (male or female) and the risk for organ failure (higher or lower) based on eCRF data. Prohibited immunosuppressive medications or immunotherapies and treatment discontinuation will be ignored (treatment policy strategy). If the re-hospitalization for acute pancreatitis status is unknown, the re-hospitalization for acute pancreatitis will be imputed as No.

The proportion and 95% CI of patients who are re-hospitalized for other causes through Day 30 will also be analyzed in a similar manner.

Protocol CM4620-203 CONFIDENTIAL Page 20 of 31

8.7.5 Change in Severity of AP by CTSI Score from Screening to Day 30

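### Re-hospitalization and composite tiers 2-4 are counted to the Day 30 visit rather than to a fixed Day 30, and the Day 30 scan has no analysis window

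*SAP*

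**What the plan says.** **Horizon.** SAP 5.1 and Protocol 2.3 list re-hospitalization as an endpoint by Day 30. SAP 8.7.4 analyses the proportion of patients "re-hospitalized for either acute pancreatitis or the development of pancreatic necrosis/necrotizing pancreatitis through the Day 30 visit". In SAP 8.9 the tiers for severe respiratory failure, necrosis of at least 30% and re-hospitalization also run to the Day 30 visit. The general rule in SAP 8.1.6 is "The study summary and analysis will be based on the eCRF visits". No analysis window or date cut-off accompanies it.

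**When the visit happens.** Protocol 8.10 and Appendix 8 give the visit ±5 days. Protocol 3.1 instead says "Patients discharged from the hospital before Day 25 will return at Day 30 (+5 days) to perform the Day 30 assessments". An early assessment is allowed: "For patients discharged from the hospital on Days 25-29, the Day 30 assessments may be performed on the Day of discharge". For patients who do not come back, the site "will continue to contact patient by phone to return for on-site visit up to eight weeks following visit date". Protocol 8.10 calls an out-of-window visit a deviation, but still asks for all the Day 30 assessments, including the scan.

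**When the scan happens.** SAP 3.1 states "Patients will receive another CECT of the abdomen/pancreas at the Day 30 (±5 days) visit". Protocol 8.10 says "Perform CECT of the pancreas. May be performed in the 5 days before or after the visit". Footnote c of Appendix 8 says "If the CECT is performed 25 to 29 days after SFISD, it will substitute for the Day 30 visit CECT scan and will be captured". Protocol 8.12.12 lets the scan be delayed for safety and gives no upper limit. Under SAP 8.7.5 and 8.7.6, unscheduled scans are used only if the Day 30 scan is missing. In that case the last one is carried forward, whatever its date.

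**The concern.** A proportion with an event by Day 30 has a clear meaning only if every patient is observed for the same time. Here the observation period ends at a visit whose date varies, and the analysis follows the visit label. The resulting rate mixes different times at risk and is still reported as a Day 30 rate.

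Two errors in opposite directions are possible. A patient assessed on Day 25 has no later study visit, so a readmission on Days 26-30 may never reach the database; SAP 8.7.4 sets unknown status to No. A patient brought back at about Day 86 has readmissions from after Day 30 counted.

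Necrosis and re-hospitalization rank above food tolerance in the composite. In a pair tied on the higher tiers and discordant on one of these, the mistimed value decides the comparison and food tolerance is not consulted. CTSI and necrosis are likewise labelled Day 30 without any rule on how far from Day 30 the scan may lie.

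**Working it through.** The documents state no figure for this point, so there is nothing to reproduce. The check is day arithmetic, followed by an illustration under stated assumptions.

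**1. Range of the visit** (Protocol 8.10)
- In window: 30 − 5 = Day 25 to 30 + 5 = Day 35.
- Late, as a deviation: 30 + 8 × 7 = Day 86 (35 + 56 = Day 91 if the eight weeks run from Day 35).

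**2. Time at risk for readmission**, for a patient assumed to be discharged on Day 5
- Visit on Day 25: 25 − 5 = 20 days.
- Fixed Day 30: 30 − 5 = 25 days.
- Visit on Day 35: 35 − 5 = 30 days.
- Visit on Day 86: 86 − 5 = 81 days.
- Ratios: 30/20 = 1.5 within the window; 81/20 = 4.05 with late recall.

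These compare individual extremes. They are not group effects.

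**3. Expected rate by visit day.** Let r be an assumed true readmission rate by Day 30 and t the days at risk.
- Constant hazard: rate = 1 − (1 − r)^(t/25).
- Declining hazard (Weibull, shape 0.5): rate = 1 − (1 − r)^√(t/25).

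| Assumed r | Hazard | Visit Day 25 | Visit Day 35 | Visit Day 86 |
|---|---|---|---|---|
| 5% | constant | 4.0% | 6.0% | 15.3% |
| 10% | constant | 8.1% | 11.9% | 28.9% |
| 10% | declining | 9.0% | 10.9% | 17.3% |
| 20% | constant | 16.3% | 23.5% | 51.5% |

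Example: r = 10%, Day 86, constant hazard gives 1 − 0.9^(81/25) = 1 − 0.9^3.24 = 28.9%.

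**4. Group rate**, for r = 10% and constant hazard. Spread visits evenly over Days 25-35: the mean rate is 9.99%, or 10.0%. Let a share s attend at Day 86 instead: rate = (1 − s) × 9.99% + s × 28.92%.
- s = 5%: 9.49 + 1.45 = 10.9%.
- s = 10%: 8.99 + 2.89 = 11.9%.
- s = 20%: 7.99 + 5.78 = 13.8%.

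The in-window spread alone hardly moves the rate, because early and late visits offset. Late recall does move it, and by less under a declining hazard.

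**5. Range of the scan.** If the ±5 days for the visit and the ±5 days for the scan around the visit add, the range is 25 − 5 = Day 20 to 35 + 5 = Day 40. It is later for recalled patients, and earlier if an unscheduled scan is carried forward. The two allowances may be meant as one. Footnote c points that way, because it treats scans before Day 25 as standard-of-care scans.

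**The case against.** The strongest case against is that little is left once the text is read closely. Visits after Day 35 are deviations, and the eight weeks describe a retention effort, not a visit window. The in-window spread leaves the group rate unchanged. Visit rules are the same in all blinded arms. Re-hospitalization is defined by Day 30, its dates are collected, and SAP 8.1.4.2 measures study time from SFISD, so a programmer could apply the right cut-off unprompted.

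Most of this stands as a limit on size. It does not remove the defect: SAP 8.7.4 and 8.9 name the visit as the end point, and nothing tells the programmer to override that. That the dates are collected shows the repair is feasible, not that it is planned.

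A reader might infer more than the documents support:
- **That every Day 30 endpoint is affected.** Protocol 10.8 takes 30-day mortality from the date of death relative to first dose, and Protocol 8.10 adds a public-records check for non-returners. Length of stay covers 30 days, the composite food tier is limited to 30 days from SFISD, and the primary endpoint uses meal dates and times. For mortality, what remains is a gap of at most five days after an early visit and the loose reference to the Day 30 visit in SAP 5.3 and 8.9.
- **That a late scan always displaces a timely one.** Footnote c lets a scan at 25 to 29 days substitute. Displacement of an in-window scan is plausible mainly for an unscheduled one around Days 30-35.
- **That a mistimed tier overrides food tolerance throughout the composite.** It does so only in pairs tied above that tier and discordant on it. The composite also scores unknown status as 0; imputation as No or alive belongs to the separate secondary analyses.
- **That the comparison of arms is biased.** Nothing in the design ties visit timing to arm. Bias would need timing to differ by arm, for example through earlier discharge, and no document shows this.

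**Conclusion.** The point holds for re-hospitalization, for composite tiers 2-4 and for the Day 30 CTSI and necrosis scan. These have no common time horizon: the visit can fall from Day 25 to about Day 86, the later part as a deviation.

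The size depends on an unknown, the share of late visits. Under the 10% constant-hazard assumption the reported rate stays at 10.0% with no late visits and reaches 13.8% if one patient in five attends at Day 86. The expected harm is noise and a rate that does not mean what its label says. The primary dose-response analysis is not materially affected. The change is still worth making, because it gives every patient one horizon at almost no cost.

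**What to change.** **Events.** In SAP 8.7.4 and 8.9, count re-hospitalization and severe respiratory failure by actual event date to SFISD + 30 days for every patient. Write the cut-off as a date formula, because SAP 8.1.4.2 numbers the SFISD date as Day 1. In SAP 5.3 and 8.9, reword the first tier as death within 30 days of SFISD.

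**Early assessments.** For anyone whose Day 30 assessment precedes Day 30, confirm vital status and readmission by one phone call at Day 30. The weekly calls already planned lead up to the visit, so this is a small added contact.

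**Scans.** In SAP 8.7.5, 8.7.6 and composite tier 3, set one analysis window, for example Days 25-35. Use the scan closest to Day 30 within it, scheduled or unscheduled. A scan outside the window should not simply be declared missing: the carry-forward rule would then bring in an unscheduled scan of any date, possibly much further from Day 30, and could miss later necrosis. Keep the late scan in the main analysis, flagged by scan day. Add a sensitivity analysis restricted to in-window scans, and report the distribution of scan days by arm.

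**Protocol wording.** Reconcile +5 with ±5 days for the visit, and the scan allowance in Protocol 8.10 with footnote c.

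**Cost.** SAP text, a little more programming, and one short call for patients seen early. No new visit is needed.
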